7 MISSING DATA

Missing data are inevitable in clinical research. Every effort has been made to minimize missing data in D2d. The primary analysis will assume that censoring for time-to-event variables is non-informative. However, we will perform sensitivity analyses to assess the degree to which the results are sensitive to the validity of the assumptions of non-informative censoring or non-informative missingness. For the secondary analyses using linear mixed effects models over time, results will be valid unless data are not missing at random.

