4. Symptom-directed physical examination will be done as needed (e.g. if adverse events are reported at a follow-up visit).
5. Vital signs include height, weight, blood pressure and heart rate.
6. Food frequency questionnaire (FFQ) will be completed at baseline, and at visits M12 and M36 only in participants free of diabetes.
7. Lifestyle counseling includes written educational materials at baseline. During the trial, participants will join the D2d Support and Education Program.
8. Laboratory and urine testing is done after 8 hours of overnight fasting.

9. Pregnancy test is required for women of reproductive potential at screening. Point-of-care urine testing will be done followed by confirmatory blood testing, if point-of-care test is positive. If point-of-care urine testing is not an option, a urine or serum test will be done at the site's laboratory. Pregnancy testing is done during the study if the participant reports missing two consecutive menstrual periods, based on the woman's typical menstrual cycle. During pregnancy, participant becomes "inactive" and resumes participation after delivery.
10. HbA1c, FPG, 2hPG and urine calcium-creatinine ratio are measured by the Central Laboratory in real time (see text for details on reporting of results). Other outcome laboratory tests (e.g. 25OHD, insulin) are done at a later time
11. At screening, HbA1c and FPG may be done by the site's local laboratory or any other laboratory (including the LCBR at U. Vermont, which serves as the study's Central Laboratory).
12. 2hPG, Glu₃₀, and insulin (Ins₀, Ins₃₀, Ins₁₂₀) are performed at baseline, and at annual visits in participants free of diabetes.
13. Semi-annual confirmatory testing: If FPG \geq 126 or HbA1c \geq 6.5% at the semi-annual visit, a confirmatory visit is conducted and only the abnormal test is repeated.
14. Annual confirmatory testing: If FPG \geq 126 or HbA1c \geq 6.5% or 2hPG \geq 200 mg/dL at the annual visit, a confirmatory visit is conducted that may include an OGTT (see text for details).
15. Letter informing participant's physician(s) of her patient's participation in D2d.
16. Letter informing participant's physician(s) of her patient's continued participation in D2d, and the outcome of glycemic testing or diabetes diagnosis according to the study's criteria.

The last scheduled visit (semi-annual or annual) serves as the end-of-study visit. Procedures done will depend upon the scheduled visit with which it coincides (see text).

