Confirmatory testing. If any one of the glycemic measures (FPG, HbA1c, 2hPG) meets criteria for diabetes during a scheduled visit, including the end-of-study visit, a confirmatory visit will be completed to repeat the measures as described in section 9. The Central Laboratory, via the EDC, will notify the clinical site of the need for confirmatory testing. A diagnosis of diabetes will be made when any two sequential glycemic measures are positive for diabetes as described in section 9.1. Numerical values will *not* be reported to the sites, participants and health care providers unless

criteria for diabetes are met at the confirmatory visit. Otherwise, the EDC system will notify the sites only that results do not meet criteria for diabetes.

To lessen the chance that participants would dramatically alter their lifestyle after a positive glycemic test on initial testing or be unduly alarmed, study personnel will emphasize to participants that an initial positive test for diabetes may often not be verified at confirmatory testing and that, rarely, repeat testing may be required for quality control purposes.

After participants reach the diagnosis of diabetes, they will continue in the study, including taking the study pills without unmasking and will complete all subsequent planned visits. OGTT and serum for insulin will not be drawn after the diagnosis of diabetes.

The following blood and urine samples will continue to be collected after diabetes diagnosis, per study schedule, and results will be provided to the site, participant and her healthcare provider(s):

- FPG
- HbA1c
- Serum calcium
- Serum creatinine
- Urine calcium-creatinine ratio

The following blood and urine samples will also continue to be collected, per study schedule, but results will not be reported to the site.

- 25OHD
- Blood and urine for storage

End-of-study visit. The end-of-study visit will coincide with a scheduled visit (semi-annual or annual), and the activities will include those that would occur at the scheduled semi-annual (i.e., FPG, HbA1c) or annual visit (e.g., FPG, HbA1c, 2hPG, serum calcium and creatinine, urine calcium-creatinine ratio, blood and urine for storage, FFQ).

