9.1 Primary Endpoint (Outcome)

The primary outcome will be *time to progression from pre-diabetes to incident (new-onset) diabetes, defined by laboratory criteria*, as follows:

Laboratory diagnosis of diabetes, based on the following ADA glyceic criteria²⁶² measured at study visits: FPG \geq 126 mg/dL, 2hPG \geq 200 mg/dL **and/or** HbA1c \geq 6.5% (Figure 9.1.1 and 9.1.2).

All three glyceic measures will be assessed at scheduled yearly visits by conducting a 75-gram OGTT (Figure 9.1.1). If all three glyceic measures are negative for diabetes, then the participant does not have diabetes and will continue on the assigned treatment. If two or all three of the glyceic measures are positive for diabetes, the participant will be considered to have reached the diabetes outcome and no confirmatory testing is required. If only FPG or HbA1c is positive for diabetes, then a confirmatory visit to repeat the *same glyceic test that was positive* will be completed within 8 weeks. If the repeat measure is also positive for diabetes, then the participant will be considered to have reached the diabetes outcome. For example, HbA1c = 6.5% and FPG = 119 mg/dL at the scheduled annual follow-up visit and HbA1c = 6.6% at the confirmatory visit. If only the 2hPG is positive for diabetes, then a confirmatory visit (with an OGTT) to repeat all three glyceic measures will be completed within 8 weeks. If the repeat 2hPG is positive for diabetes, then the participant will be considered to have reached the diabetes outcome. If the repeat 2hPG is negative for diabetes but *both* repeat HbA1c and FPG are positive for diabetes, then the participant will be considered to have reached the diabetes outcome. Otherwise, the participant does not have diabetes and will continue on the assigned treatment.

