Fasting plasma glucose and HbA1c will be assessed at scheduled semi-annual visits (Figure 9.1.2). If both glyceic measures are negative for diabetes, then the participant does not have diabetes and will continue on the assigned treatment. If both glyceic measures are positive for diabetes, the participant will be considered to have reached the diabetes outcome and no confirmatory testing is required. If only one of two glyceic measures (FPG or HbA1c) is positive for diabetes, then a confirmatory visit to repeat the *same glyceic test that was positive* will be completed within 8 weeks. If the repeat measure is also positive for diabetes, then the participant will be considered to have reached the diabetes outcome. For example, HbA1c = 6.3% and FPG = 127 mg/dL at the scheduled semi-annual follow-up visit and FPG = 129 mg/dL at the confirmatory visit.

[figure not shown]
At any time when symptoms consistent with hyperglycemia are reported, FPG and HbA1c will be measured, outside of a scheduled study visit. The algorithm for the semi-annual visit, described above, will be followed.

At the end-of-study visit, the procedures for the scheduled (semi-annual or annual) visit will be completed and the respective algorithm (Figures 9.1.1 and 9.1.2) will be followed to assess for incident diabetes.

Blood for plasma glucose (FPG, 2hPG) and HbA1c will be drawn locally and shipped to the Central Laboratory for measurements. Results will be available to the site typically within 5 business days from day of shipment. The date of onset of diabetes is defined as the date of the first diagnostic glyceic value. When diabetes is diagnosed, study pills will be continued without unmasking and participants will continue in the study and complete all subsequent planned visits.

[figure not shown]
Tests for glycemia will be performed without interrupting the assigned treatment. Testing at one of the scheduled follow-up visits or confirmatory visits will be postponed for up to 8 weeks if a temporary concomitant condition exists that would affect glucose tolerance (e.g. active infection, hospitalization which may also require temporary use of a diabetes medication), its assessment (e.g. blood transfusion or blood donation) or for any other administrative or social reason.

Figure 9.1.1. Flow diagram of laboratory evaluation for diabetes at the annual visit

¹During the annual OGTT, the following will also be drawn: insulin at 0, 30 and 120 minutes and glucose at 30 minutes

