When the participant meets a laboratory criterion for diabetes, the Central Laboratory will notify the collaborating site of the results and the need for repeat confirmatory testing via the electronic web-based data capture system. After the primary outcome has been reached (by D2d criteria or adjudication), participants will continue in the study, including taking the study pills without unmasking and will be referred to their physician for further care in relation to diabetes. Participants will continue to return for scheduled visits until the end of the study for assessment of other outcomes. At the annual visits, the HbA1c and FPG will be collected but the 75-gram OGTT for 2hPG will not be collected.

Figure 9.2.1. Flow diagram of evaluating self-reported physician-diagnosis of diabetes or initiation of diabetes-specific pharmacotherapy between scheduled visits.

- In lieu of an Unscheduled Confirmatory (UNCO) visit, a regular D2d visit may be done provided the visit window is approaching

Figure 9.2.2. Flow diagram for (planned or actual) use of diabetes-specific pharmacotherapy between scheduled visits.

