3.2.1 Secondary outcomes – related to the primary outcome: continuous variables

- HbA1c (measured at baseline, semi-annually)
- FPG (baseline and semi-annually)
- 2hPG (baseline and annually)
- Insulin secretion, Insulin sensitivity and Disposition Index (indices from OGTT; baseline and annually)

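### 2hPG and the OGTT insulin indices stop at diabetes diagnosis, so mixed models for them that omit FPG and HbA1c are unlikely to meet the missing-at-random condition in SAP 7

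*SAP*

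**What the plan says.** **The stop.** Protocol 8.2.3: "OGTT and serum for insulin will not be drawn after the diagnosis of diabetes". Protocol 9.1 repeats it: "At the annual visits, the HbA1c and FPG will be collected but the 75-gram OGTT for 2hPG will not be collected". Note 12 to the Schedule of Procedures says that 2hPG, 30-minute glucose and insulin "are performed at baseline, and at annual visits in participants free of diabetes".

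**What triggers it.** Protocol 9.1, semi-annual visits: "Fasting plasma glucose and HbA1c will be assessed at scheduled semi-annual visits". No 2hPG is taken there, and "If both glyceic measures are positive for diabetes, the participant will be considered to have reached the diabetes outcome and no confirmatory testing is required". One positive test leads to a confirmatory visit that repeats only that test. Annual visits: "All three glyceic measures will be assessed at scheduled yearly visits by conducting a 75-gram OGTT". A lone positive FPG or HbA1c is again confirmed by repeating that test, so diabetes can be diagnosed with a negative 2hPG.

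**The analysis.** SAP 3.2.1 lists 2hPG and "Insulin secretion, Insulin sensitivity and Disposition Index (indices from OGTT; baseline and annually") as secondary outcomes. SAP 5 analyses change from baseline with a linear mixed model that allows for within-person correlation. It mentions neither a joint model nor auxiliary variables. SAP 7 says of these models that "results will be valid unless data are not missing at random". It also promises sensitivity analyses of non-informative censoring and missingness, without naming a method, outcome or variables. Neither document says whether the target for 2hPG or insulin includes values after diagnosis.

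**The concern.** A likelihood-based mixed model allows for missing values whose absence is explained by data in the model. Here later 2hPG and insulin values are absent because a diagnosis was made, and FPG and HbA1c often make it. A model holding only the history of 2hPG, or only that of an insulin index, does not contain those variables. Missing at random then fails for that model, unless FPG and HbA1c say nothing about later 2hPG or insulin beyond what the outcome's own history says. For correlated glycaemic markers that is unlikely.

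If the treatment works, diagnosis is more common on placebo, so the loss is unequal between arms. What is at stake is the estimated effect on 2hPG, insulin secretion, insulin sensitivity and disposition index, which are secondary aims in Protocol 3.2.2. The primary endpoint is not affected.

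**Working it through.** **1. The plan's own figures.** The documents give no power or bias figure for 2hPG or insulin. The relevant figures are the expected diagnoses in Protocol 11.1, Table 1. Inputs from 11.1: 2,382 randomized 1:1, so N = 1,191 per arm; placebo hazard λ = 0.1054; loss hazard μ = 0.0513; hazard ratio 0.75, so λ = 0.75 × 0.1054 = 0.07905 on vitamin D.

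Diagnoses by M06 = N × λ/(λ+μ) × (1 − exp(−(λ+μ)/2)).
- Placebo: 1,191 × 0.1054/0.1567 × (1 − exp(−0.07835)) = 60.4. Table 1: 60.4.
- Vitamin D: 1,191 × 0.07905/0.13035 × (1 − exp(−0.065175)) = 45.6. Table 1: 45.6.

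The M06 to M24 entries are reproduced to 0.1 event. The totals come out at 298 and 232 against 293 and 228.

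**2. Who is affected (from Table 1).**
- Diagnosed in all: 293/1,191 = 24.6% on placebo, 228/1,191 = 19.1% on vitamin D.
- Diagnosed at M06 to M18, so with no M24 OGTT: 60.4 + 55.9 + 51.7 = 168.0 (14.1%) against 45.6 + 42.7 + 40.0 = 128.3 (10.8%).
- Diagnosed at M06, before any follow-up OGTT: 60.4 against 45.6. If change from baseline is the response, these participants contribute nothing to a model without FPG and HbA1c.
- Placebo diagnoses at the visits without an OGTT (M06, M18, M30, M42): 60.4 + 51.7 + 33.1 + 9.4 = 154.6 of 293 (53%). Table 1 assumes constant hazards. The true share may be lower, because annual visits add the 2hPG test.

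**3. Size of the bias.** This needs SDs, slopes and correlations that the documents do not give, so all of these are assumptions. FPG, HbA1c and 2hPG were simulated for 250,000 to 300,000 people per arm with personal intercepts, slopes and visit noise. The protocol's diagnostic rules were applied and 2hPG was stopped at diagnosis. The model had arm-by-visit means and an unstructured covariance. Entries are the mean difference in 2hPG (mg/dL) over M12, M24 and M36, without post-diagnosis drugs.

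| Assumed effect; slope correlation; intercept correlation | 3-year incidence, placebo / vitamin D | HR | Complete data | 2hPG alone | With FPG and HbA1c |
|---|---|---|---|---|---|
| None; 0.8; 0.3 | 27.9% / 27.9% | 1.00 | 0.00 | 0.00 | 0.01 |
| Level; 0; 0.1 | 34.1% / 26.8% | 0.75 | −6.15 | −6.06 (1.5% smaller) | −6.06 |
| Level; 0.5; 0.3 | 30.7% / 24.3% | 0.76 | −6.18 | −5.86 (5.2%) | −6.06 |
| Level; 0.8; 0.3 | 27.9% / 22.3% | 0.77 | −6.18 | −5.81 (6.0%) | −6.12 |
| Slope; 0.8; 0.3 | 27.9% / 17.6% | 0.59 | −9.10 | −8.65 (4.9%) | −9.03 |

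Over all settings run, the 2hPG-only model was 1% to 6% too small and the joint model about 1% to 2%. When the slopes are uncorrelated, the joint model gains almost nothing. The loss builds up over time: in the fourth row, at M36 alone, the figures are −6.11 with complete data, −5.28 from 2hPG alone (1 − 5.28/6.11 = 14% smaller) and −5.96 jointly (2%).

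A second simulation of the same rules, with a hazard ratio of about 0.7, gave 4% to 7% for 2hPG and 2% to 5% for a disposition-type index. Both fell to about 2% to 3% with FPG and HbA1c included.

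**4. Dependence on the target.** Suppose the target includes 2hPG under diabetes drugs begun after diagnosis. The 2hPG-only estimate is then 5% to 6% too small if drugs lower 2hPG by 0 mg/dL, 1% to 3% too large at 20 mg/dL, and 10% to 13% too large at 40 mg/dL.

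**The case against.** - **The sentence in SAP 7 is conditional.** It states the assumption and does not assert that it holds, and sensitivity analyses are promised. Both points are fair. But the protocol's own rule makes the condition doubtful for these outcomes, and the promise specifies nothing.
- **Part of the stopping is harmless.** When an observed 2hPG at an annual visit makes the diagnosis, the 2hPG model contains the cause. This stands, and it is one reason the bias is modest. Nor do the worst progressors drop out of the analysis, because their values up to diagnosis remain. In the third row of the table a plain available-case comparison gave −5.26, which is 15% too small (1 − 5.26/6.18), against 5.2% for the mixed model.
- **Separate models are inferred.** SAP 5 does not say that each outcome is modelled alone. That is the natural reading of the text, and nothing there brings in FPG or HbA1c.
- **Consequence.** These are secondary outcomes, some reserved for later papers, and the runs with no effect showed no bias. This limits the weight of the point.

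A reader might infer that the planned models simply understate the effect. The documents do not support that. It needs a true benefit and a target without post-diagnosis drugs. Protocol 9.1 refers diagnosed participants for diabetes care, and the direction can reverse if treated values belong to the target.

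A reader might also expect a larger overall loss. A small simulation (12 replicates per run, correlation 0.3, true difference about −10 mg/dL) gave 12% to 14%. Its Monte Carlo error is not known, its effect size appears nowhere in the documents, and the larger runs do not reproduce it for the average over visits.

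**Conclusion.** The point holds in a limited form. The stop is planned, FPG and HbA1c can cause it without a 2hPG, and the described models for 2hPG and the insulin indices leave both markers out. Missing at random is therefore unlikely to hold for those models.

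If vitamin D works and the target excludes drug treatment after diagnosis, the average effect is attenuated by roughly 1% to 7%, and by more at the last visits. With no effect there is no bias. These sizes rest on assumed SDs, slopes, correlations and treatment shifts. The insulin side rests on one simulated disposition-type index, so its size is less certain than that for 2hPG. The point is worth acting on because SAP 7 does not address a known design feature and the data needed are already collected.

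**What to change.** In SAP 5.1 and 7:

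1. State that the OGTT and insulin sampling stop at diagnosis, and that the target for 2hPG and the insulin indices is the effect without diabetes treatment begun after diagnosis.
2. Analyse these outcomes with all FPG and HbA1c values up to and including diagnosis as auxiliary outcomes: scheduled, unscheduled and confirmatory. Confirmatory values matter because a single positive test becomes diabetes only through them. For the insulin indices add 2hPG, which is itself a trigger.
3. Use either a joint repeated-measures model, or multiple imputation by arm followed by the planned mixed model. Name this in place of the general sensitivity promise for these outcomes.

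The cost is SAP text, some programming and a more complex model. No visits, samples or participants are added. A small bias may remain. FPG and HbA1c are not measured at M03 and can be absent when a semi-annual visit is held by phone (Protocol 7.4). Diagnoses adjudicated on outside laboratory values also stay outside the model, although Protocol 9.1 expects fewer than 5% of outcomes to rest on adjudication alone.
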